#### 6.4 Primary Endpoint Analysis

The primary endpoint of PROs at Week 12 will be assessed descriptively, using the FAS dataset.

For ASIS questionnaire, the individual item and domain/subscale scores will be created per instrument developer instructions, analyzed descriptively for the baseline and Week 12 encounters, treating the responses as categorical variables and/or continuous variable, as appropriate. For the overall questionnaire data evaluation, no missing data imputation will be applied to compute domain/subscale scores.

The Patient Global Assessment (PtGA) of acne severity based on the single ASIS item (# 9) will be analyzed separately using descriptive statistics and reported for Week 12. Specifically, proportion of Subjects who reported clear (0) and almost clear (1) on the item scale at Week 12 will be assessed. Last Observation Carried Forward (LOCF) data imputation method will be used to impute responses to ASIS item # 9 at Week 12 for the Subjects with missing data at Week 12.

Patient self-rating of their appearance based on the single ASIS Item (# 10) will be analyzed separately using descriptive statistics and reported for Week 12. Specifically, proportion of Subjects reporting "very good" or "excellent" at Week 12 will be assessed. LOCF data imputation method will be used to impute responses to ASIS item # 10 at Week 12 for the Subjects with missing data at Week 12.

For EPQ, the items will be analyzed individually using descriptive statistics and reported for Week 12.

For all PRO elements, descriptive statistics will be computed. ASIS summary domain scores, ASIS item # 9, ASIS item # 10, and individual EPQ items will be stratified by age and other subgroups outlined in Section 6.3.2, to explore the relationship between these HRQoL items and subject characteristics.

## 6.5 Secondary Endpoint Analysis

The secondary endpoint of the study is the proportion of Subjects with Facial IGA success at Week 12, defined as  $\geq 2$ -point decrease in IGA score from baseline and a score of 0 (clear) or 1 (almost clear) at Week 12. The analyses of IGA success will be conducted for the overall cohort (using the FAS dataset). LOCF data imputation method will be used to impute responses at Week 12 for the Subjects with missing data at Week 12. Relationship between this endpoint (with LOCF imputation) and subject characteristics will be explored using descriptive analyses, by leveraging subgroup analysis outlined in Section 6.3.2.

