## 2 PROSES STUDY OBJECTIVES

### 2.1 Study Objectives

The primary objective of the study is to evaluate PROs in terms of health related quality of life (HRQoL) among patients with moderate to severe non-nodular AV who are administered sarecycline in real-world community practice settings in the U.S. The secondary objective is to evaluate effectiveness of sarecycline treatment, measured by Investigator Global Assessment (IGA) of AV severity on the face.

The additional study objectives include the following evaluations among study Subjects and Site Investigators\*:

- Investigator satisfaction with their sarecycline treatment outcomes.
- Safety and tolerability of sarecycline.
- Comparison of Investigator and Subject perceptions of AV severity.

Note: Dermatologists are expected to predominantly constitute the Site Investigator category, while a few physician assistants and nurse practitioners may be included in the study, reflecting the routine care management of acne in community practice settings.

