## 3 STUDY DESIGN

This is a single-arm, prospective cohort study which will enroll patients with moderate to severe acne vulgaris (AV) who are prescribed sarecycline in real-world community practices in the U.S. Caregivers also enrolled in the study, in case of pediatric patients. Study Subjects were followed for up to 12 weeks post-index date (with the 'index-date' defined as the date of initiation of sarecycline). Study Site Investigators and Subjects completed online surveys at baseline (at time of study enrollment) and at weeks 4, 8 and 12, post-index date.

This study entailed provision of sarecycline treatment to study participants. Site Investigators decided on who to prescribe sarecycline as part of usual care, based on their best clinical judgment, prior to subject recruitment. The study is sponsored by Almirall, hereinafter referred to as the

Sponsor. The study is managed by Avant Health, hereinafter referred to as the Contract Research Organization (CRO).

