### **3.2 Subject Exclusion Criteria**

An individual who meets any of the following criteria were excluded from participation in this study:

- Patients with any dermatological or physical condition of the face that could interfere with the AV clinical evaluations.
- Patients with any history of allergy to tetracycline-class antibiotics, pseudomembranous colitis or antibiotic-associated colitis.
- Patients with any known resistance to other tetracyclines.
- Patients currently treated with any of the following: penicillin, oral retinoids (incl. Isotretinoin and acitretin).
- Among female Subjects: Currently pregnant, lactating, or is planning a pregnancy during the study period.
- Patients or their caregivers are unable to comply with the requirements of the study or patients who in the opinion of the Site Investigator should not participate in the study.
- Patients for whom medical chart is inaccessible to Site Investigators to complete baseline data collection.

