#### **5.3.1 *Investigator Assessments***

An IGA scale of 0 (Clear) to 4 (Severe) was used by the Site Investigators to assess the severity of a subject's facial acne at the time of study encounters. The IGA is representative of the investigator's overall general assessment of the subject's Acne and takes into account the quality, as well as the quantity, of lesions. These assessments were done at baseline encounter to document AV severity before initiation of sarecycline treatment; the assessments were repeated by the Site Investigators at study subject follow-up encounters at Weeks 4, 8 & 12, post-index

date. The comparison of follow-up assessments to the baseline assessment will help determine treatment effectiveness. All Investigator assessments were conducted via in-person visits/encounters at baseline and week-12. The same evaluator performed all evaluations for a subject during the study.

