### **6.3.2 *Subgroup Analysis***

Primary and select additional outcome measures (as individually identified in the following sections) will be summarized and repeated for the following subgroups, using FAS:

- Gender: male and female
- Age groups: 9 to 17 years and  $\geq 18$  years
- Race: white, african-american/black, other

- Body mass index: < 25 kg/m^2 and ≥ 25 kg/m^2
- Baseline facial IGA score: moderate and severe
- Concomitant use of contraceptives in females: yes and no

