## 6.7 Prior and Concomitant Medications

Medication usage is coded using the latest (2022) WHO Drug Dictionary. Medications are presented by WHO Drug Anatomical/Therapeutic/Chemical (ATC) category and WHO Drug preferred name. Summaries are presented for prior (prior to the first dose of study treatment, gathered as aggregate indicators as well as at individual item level) medication use and concomitant (after first dose of study treatment had been given, gathered at individual item level) medication use. Medications with an end date occurring before the first study treatment (sarecycline) dose date in the treatment period are identified as prior medications. Medications with a start date occurring on or after the first study treatment (sarecycline) dose date in the treatment period or medications with a start date prior to the first (sarecycline) dose that were ongoing or with end dates that were on or after the first treatment (sarecycline) start date are identified as concomitant medications.

Concomitant Acne and non-Acne medications are captured at Baseline and at the study end (Week-12) to characterize the use of concomitant medications among the study cohort. Accordingly, the Acne and non-Acne concomitant medication use will respectively be summarized in aggregate for the 3-month study observation period, and not separated by study visits.

Contraceptive medications (part of non-Acne concomitant medications) will be grouped into single class/group of medications, irrespective of the route of administration or active ingredients, as reported from patient medical charts.

All summaries present the number (%) of subjects for each medication. The denominators for calculating the percentages are based on the number of subjects in the FAS population.

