**Table 7.2.6.2 Acne Concomitant Medication Use**

Character	N=X
Has not use any acne medication	n (%)
Topical medication	
Topical retinoids	n (%)
Salicylic acid	n (%)
Benzoyl peroxide	n (%)
Topical antibiotics	n (%)
Topical Dapsone	n (%)
Azelaic acid	n (%)
Topical Clascoterone	n (%)
Other (total)	n (%)
A	n (%)
B	n (%)
C	n (%)
Oral medication	
Oral antibiotics (tetracycline or macrolide)	n (%)
Anti-androgen agents	n (%)
Oral antibiotics (non-tetracycline class)	n (%)
Isotretinoin	n (%)
Other	n (%)
A	n (%)
B	n (%)
C	n (%)
Oral contraceptives (any type)	n (%)
Other therapies	
Light therapy	n (%)
Drainage and extraction	n (%)
Chemical peel	n (%)
Steroid injection	n (%)
Other	n (%)

Note: Data from Clinician DCF; X patients had missing data; The denominator for the percentages is the number of patients with available data (N=X)

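### Facial IGA success is read as sarecycline effectiveness in a single arm, but no planned analysis relates it to other acne treatment, although that use is recorded and dated against the first dose

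*SAP*

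**What the plan says.** SAP 2.1 states the aim: "The secondary objective is to evaluate effectiveness of sarecycline treatment, measured by Investigator Global Assessment (IGA) of AV severity on the face". SAP 3 describes a single-arm cohort, and SAP 5.3.1 says how effectiveness is to be judged: "The comparison of follow-up assessments to the baseline assessment will help determine treatment effectiveness". SAP 6.5 analyses the proportion with IGA success at Week 12 in the overall FAS and, on further breakdown, says: "Relationship between this endpoint (with LOCF imputation) and subject characteristics will be explored using descriptive analyses, by leveraging subgroup analysis outlined in Section 6.3.2".

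The 6.3.2 list covers gender, age, race, body mass index, baseline IGA and one medication item: "Concomitant use of contraceptives in females: yes and no". Table 7.2.4.8 follows that list. SAP 6.11 adds results with and without LOCF and, if some visits are remote, a split by visit type.

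On other acne treatment:

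- SAP 3.2 bars only current penicillin and oral retinoids at entry. Topical agents, other oral antibiotics, anti-androgens and procedures are not named.
- Protocol 7.5 has the investigator record, at Week 12, changes in acne medication since baseline.
- SAP 6.7 compares start and end dates with the first sarecycline dose. It then summarises use in aggregate over the study period, in Table 7.2.6.2, "Acne Concomitant Medication Use".
- Neither document says how acne treatment started during follow-up is handled when IGA success is counted.

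**The concern.** Without a comparator, change from baseline absorbs everything that acts on the face over 12 weeks. Other acne treatment is aimed at the very outcome being measured, and it is recorded. The SAP accepts that a co-medication can be worth a split, but the one it chose is contraceptives, which 6.7 classes as non-acne medication and pools over all routes. Drugs given for acne itself are left out.

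Table 7.2.6.2 will show how common such treatment was, but not whether success was concentrated among its users or its non-users. The reported rate will be read as sarecycline effectiveness, with no means of judging how far co-treatment contributed.

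**Working it through.** **Is there a figure to reproduce?** No. SAP 6.1 reports no sample size or power calculation. Neither document gives an expected success rate, a rate of other acne treatment, or its effect on IGA. Every percentage below is an assumption, apart from the planned 300 subjects.

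**Does any planned output link the two?** IGA success appears in Tables 7.2.4.3, 7.2.4.7, 7.2.4.8 and 7.5.1. The first two are overall, the third uses the 6.3.2 list, and the fourth splits by visit type. Table 7.2.6.2 has no outcome column. Protocol 12.3.3 foresees multivariate models with baseline characteristics and other variables such as adherence, where feasible. It does not name acne co-treatment, and the SAP has no corresponding section. So no output makes the link.

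**Can the data support it?** Yes. The 6.7 definition of a concomitant medication pools two groups: drugs begun before the first dose and still in use, and drugs begun on or after it. The dates that define the pool also separate the groups.

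**How far could the overall rate differ from the rate without co-treatment?** Let c be the share using other acne treatment, p1 success among users and p0 success among non-users. The overall rate is (1 − c) × p0 + c × p1, so it differs from p0 by c × (p1 − p0). With p0 assumed at 50%:

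| c | p1 = 70% | p1 = 30% |
|---|---|---|
| 20% | 0.8 × 50 + 0.2 × 70 = 54% (+4) | 0.8 × 50 + 0.2 × 30 = 46% (−4) |
| 40% | 58% (+8) | 42% (−8) |
| 60% | 62% (+12) | 38% (−12) |

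Both signs are plausible. Effective co-treatment pushes p1 up. Adding treatment mainly for poor responders pushes it down.

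**Against sampling error.** At n = 300 and 50% success, the 95% half-width is 1.96 × √(0.5 × 0.5 / 300) = 5.7 points. A 4-point shift lies inside that; 8 or 12 points lie outside.

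**Precision after a split.** At an assumed 30% use, 300 subjects divide into 210 without and 90 with. The half-widths at 50% success are 1.96 × √(0.25 / 210) = 6.8 and 1.96 × √(0.25 / 90) = 10.3 points. If attrition left 240 in the FAS (also assumed), the groups would be 168 and 72, with half-widths of 7.6 and 11.5.

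**Counting starters as non-successes.** If a share s starts new acne therapy and a proportion q of them would otherwise count as successes, the rate falls by s × q. With s from 2% to 20% and q from 40% to 80%, the fall runs from 0.02 × 40 = 0.8 points to 0.20 × 80 = 16 points.

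**The case against.** The study describes usual care: clinicians manage patients as they ordinarily would, SAP 6.3.1 calls its p-values exploratory, and there is no power calculation. On those terms the all-patient success rate is a coherent estimate and not an error. That stands, and it is why the main result should not change.

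A split also would not isolate sarecycline. Natural course and regression to the mean remain after entry at IGA 3 or 4, and users and non-users are not comparable. Restricting to patients who started nothing new would condition on a post-baseline event. If treatment is added for poor response, that subset is enriched for responders. This stands too. It argues for a split on use at first dose, and for keeping starters in the denominator.

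Three stronger readings are tempting, and the documents support none of them:

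- **That isotretinoin is allowed once a patient is enrolled.** No text permits it. Oral retinoids are an entry exclusion, and Protocol 6.4.1 lets the investigator end participation when an exclusion criterion newly arises. SAP 6.2 then puts anyone terminated before Week 12 outside the FAS. The isotretinoin row in Table 7.2.6.2 repeats the row list of the prior-treatment Table 7.2.6.1, and shows neither permission nor use. Termination is discretionary, however, so the three places do not fully agree.
- **That the reported rate is inflated.** The sign of p1 − p0 is unknown.
- **That co-treatment is the only other influence the data can show.** Contraceptive use is recorded and already split.

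**Conclusion.** The point holds as an omission in the secondary analysis. IGA success is the stated measure of sarecycline effectiveness in a single arm, most other acne treatment is not barred at entry, and its timing is on record, but no subgroup, sensitivity analysis or table relates the two.

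The consequence is that success under sarecycline cannot be distinguished from success under sarecycline plus other acne treatment. The possible gap is −12 to +12 points, assuming 20–60% users and a success difference of −20 to +20 points. The documents fix neither input, so this is a range of what could be hidden and not an estimate of bias. A reader might infer that the split rate would be the sarecycline effect. It would not; it would describe how much success occurred without other acne treatment.

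**What to change.** Before database lock:

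1. In SAP 6.3.2 add a subgroup for acne medication ongoing at the first sarecycline dose (no / yes), using the 6.7 dates. Carry it into Table 7.2.4.8 for IGA success and Table 7.1.11 for ASIS domain scores at Baseline and Week 12. State whether oral contraceptives count: Table 7.2.6.2 lists them, while 6.7 places contraceptives under non-acne medication.
2. Report the number of patients who start new acne therapy after the first dose.
3. In SAP 6.11 add one sensitivity analysis that keeps patients who start new acne therapy before Week 12 in the denominator and counts them as IGA non-successes.
4. Label these results descriptive and non-causal, and keep the all-patient usual-care estimate as the main result.
5. Reconcile the exclusion in SAP 3.2, the discretionary withdrawal in Protocol 6.4.1 and the isotretinoin row in Table 7.2.6.2.

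No new data are needed. The cost is a few table rows, one added sensitivity result, wider intervals in the split groups and a sensitivity figure that may be less favourable than the main one.

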### **12.3.3 Multivariate Analyses**

CFB in key study outcome measures at Week 12 post-index date, and at Weeks 4 and 8 (if applicable) post-index date will be assessed using relevant multivariate analyses, adjusting for subject baseline characteristics and other variables (such as medication adherence) to discern the factors influencing these outcomes, as feasible. Repeated measures analyses with covariates may be used to statistically test the changes/trends for relevant outcome measures over time.

Pearson correlation coefficients may be used to assess the correlation between key outcome measures; this may also inform the consideration of covariates in select multivariate analyses (to reduce multicollinearity).

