## 12.5 Secondary Endpoint Analysis

The secondary endpoint of the study is the proportion of patients with Facial IGA success at Week 12, defined as a 2-point decrease in IGA score from baseline and a score of 0 (clear) or 1 (almost clear). The analyses of IGA success will be conducted for the overall cohort (using FAS), as well as stratified by age and other relevant subgroups. Relationship between this endpoint and subject characteristics will be explored using descriptive analyses. LOCF data imputation method will be used to impute responses at Week 12 for the Subjects with missing data at Week 12.

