### **3.1 Subject Inclusion Criteria**

**Patient Inclusion Criteria:** In order to be eligible to participate in this study, an individual must meet all of the following criteria:

- Male or female, aged 9 years and above at the time of study recruitment.
- Has facial non-nodular AV with IGA score of moderate (3) or severe (4).
- Considered as a potential candidate for sarecycline treatment to manage their AV, per clinician's judgment.
- Able to read and write English.
- Provide consent (in case of adult patients) or assent (in case of pediatric patients) to participate in the study.
- Willing to comply with all study procedures and be available for the duration of the study.

**Caregiver Inclusion Criteria:** In order to be eligible to participate in this study, an individual must meet all of the following criteria:

- Male or female, aged 18 years and above.
- Able to read and write English.
- Primary caregiver of the study-eligible patient.
- Provide consent to participate in the study.
- Willing to comply with all study procedures and be available for the duration of the study.

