**Table 7.2.4.8. Sub-group Analysis of Facial IGA Success (with LOCF imputation)**

% IGA Success		Week 12 (N=x)
Sex		
Male	n (%)	
Female	n (%)	
p-value	p	
Age Group		
≥ 9 and < 12 years	n (%)	
≥ 12 and < 18 years	n (%)	
≥ 12 years	n (%)	
p-value	p	
Race		
White	n (%)	
African America/Black	n (%)	
Other	n (%)	
p-value	p	
Body mass index		
< 25 kg/m 	n (%)	
≥ 25 kg/m 	n (%)	
p-value	p	
Baseline facial IGA		
Moderate	n (%)	
Severe	n (%)	
p-value	p	
Female who used oral contraceptive*		
Used	n (%)	
Did not use	n (%)	
p-value	p	

Note: Data from Clinician DCF; X patients had missing data; The denominator for the percentages is the number of patients with available data (N=X).

\* The denominator for the percentages is the number of 'female' patients with available data (N=X)

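### IGA success takes a 2-grade fall from moderate acne but a 3-grade fall from severe acne, so the planned subgroup p-values for this endpoint partly reflect baseline severity and need a shift table and a severity-adjusted comparison beside them

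*SAP*

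**What the plan says.** - **Scale and entry.** SAP 5.3.1: "An IGA scale of 0 (Clear) to 4 (Severe) was used by the Site Investigators". SAP 3.1 admits only patients scored 3 (moderate) or 4 (severe).
- **Endpoint.** SAP 6.5 defines success as a ≥2-"point decrease in IGA score from baseline and a score of 0 (clear) or 1 (almost clear) at Week 12". Protocol 12.5, SAP 2.2 and the notes to SAP Tables 7.2.4.3, 7.2.4.7 and 7.5.1 give a 2-point decrease without the ≥ sign.
- **Subgroups.** SAP 6.5: "Relationship between this endpoint (with LOCF imputation) and subject characteristics will be explored using descriptive analyses, by leveraging subgroup analysis outlined in Section 6.3.2". One of the factors in SAP 6.3.2 is "Baseline facial IGA score: moderate and severe".
- **Output.** Table 7.2.4.8 gives n (%) and one p-value per factor: sex, age, race, BMI, "Baseline facial IGA" and contraceptive use. SAP 6.3.1 assigns an unadjusted chi-square test to such comparisons. It calls the p-values exploratory and not for hypothesis testing, with 0.05 or below considered significant.
- **Adjustment.** Protocol 12.3.3 foresees, where feasible, multivariate analyses of change from baseline in key outcomes, "adjusting for subject baseline characteristics and other variables (such as medication adherence) to discern the factors influencing these outcomes". It does not name IGA success, and the SAP has no corresponding section or table.

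**The concern.** The same 2-grade improvement counts as a success from moderate (3 to 1) and as a failure from severe (4 to 2). A p-value on the moderate-versus-severe row can therefore be small when the two groups improve equally in grades. The crude tests for the other factors can inherit part of that gap if, say, one sex has more severe patients.

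No planned IGA output separates the two explanations. Tables 7.2.4.1 and 7.2.4.4 give the IGA distribution at each visit for the whole cohort. Tables 7.2.4.2 and 7.2.4.6 give whole-cohort changes in proportion. Table 7.2.4.5 splits by baseline IGA but uses the same 0/1 cut. Nothing crosses baseline with Week-12 IGA or shows grade change by baseline grade. At stake is the reading of the relationship between this endpoint and patient characteristics, not the overall success proportion.

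**Working it through.** The plan states no rate, power or severity mix for this endpoint, so there is no figure to reproduce. Step 1 follows from the definitions. Steps 2 to 4 use assumed inputs.

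**Step 1. Enumerate the definition (≥2-point fall and Week-12 score 0 or 1).**

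| Baseline | Week-12 scores that succeed | Smallest fall that succeeds | If read as exactly 2 points |
|---|---|---|---|
| 3 | 0, 1 | 2 | only 1 |
| 4 | 0, 1 | 3 | none |

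The ≥2-point clause never binds: for every eligible patient, success equals IGA 0/1. If the unsigned wording were programmed literally, no severe patient could succeed and a 3-to-0 patient would fail.

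**Step 2. Uniform falls.** If everyone falls 0 or 1 grade, success is 0% in both strata. If everyone falls 3, it is 100% in both (3 to 0, 4 to 1). Among these uniform cases only a fall of exactly 2 separates the strata (100% v 0%). The gap therefore depends on how many patients fall exactly 2 grades.

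**Step 3. Moderate versus severe with equal grade falls.** Assume the same distribution in both strata: no fall 15%, one grade 25%, two 40%, three or more 20%.

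- Moderate: P(fall ≥2) = 0.40 + 0.20 = 0.60.
- Severe: P(fall ≥3) = 0.20.
- With 220 moderate and 30 severe patients (assumed), a two-sided 0.05 test of 60% v 20% rejects about 99% of the time.

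Other assumed distributions, for falls of 0, 1, 2 and ≥3 grades:

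| Distribution | Moderate | Severe | Gap |
|---|---|---|---|
| 20/40/28/12% | 40% | 12% | 28 points |
| 10/25/40/25% | 65% | 25% | 40 points |
| 5/15/40/40% | 80% | 40% | 40 points |

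Across these three, with 200 to 300 patients of whom 10% to 30% are severe, the chance of p ≤ 0.05 runs from 76% to over 99%.

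Equal falls are an assumption. If 55% of moderate patients fall ≥2 grades and 60% of severe patients fall ≥3, success is 55% v 60%, in favour of severe.

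**Step 4. Other factors, through severity mix alone.** Suppose the factor has no effect of its own and success is 60% (moderate) and 20% (severe). The difference between two subgroups is then (difference in severe share) × (0.60 − 0.20). With 125 patients per subgroup:

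| Severe share | Success | Difference | Chance of p ≤ 0.05 |
|---|---|---|---|
| 10% v 20% | 0.9×0.6 + 0.1×0.2 = 0.56; 0.8×0.6 + 0.2×0.2 = 0.52 | 4 points | about 10% |
| 10% v 30% | 0.56; 0.7×0.6 + 0.3×0.2 = 0.48 | 8 points | about 24% |

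Over the three distributions in Step 3, with 125 to 150 per subgroup, these two mixes give 2.8 to 4.0 points (7% to 12% rejection) and 5.6 to 8.0 points (15% to 34%). A wide imbalance of 5% v 35% gives 8.4 to 12 points (29% to 64%). With equal mixes the effect is nil.

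**The case against.** The strongest reply is that the table answers the question SAP 6.5 asks. Success is one end state for everyone, and who reaches it by baseline severity is a fair descriptive question. The study is single-arm, the p-values are labelled exploratory, and nothing in the SAP plans to conclude that sarecycline works less well in severe acne. Protocol 12.5 also asks only for descriptive analyses of IGA success, and protocol 12.3.3 concerns change from baseline where feasible. Table 7.1.11 shows mean ASIS domain scores by baseline IGA, so the primary outcome has a graded view by severity. All the rejection rates above rest on assumed inputs. A ≥2-grade decrease is not neutral either: it credits 4 to 2, which is still mild, while a moderate patient must reach 0 or 1.

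Most of this stands, and it limits the point. A reader might infer that the definition decides the severity comparison, or that severe patients must look worse whenever everyone improves equally. The documents support neither: uniform falls of 0, 1 or 3 grades give equal success, and severe patients may fall further. Nor do the documents make adjustment of IGA success a protocol commitment that the SAP dropped.

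The reply does not remove the tilt. Under equal, mixed grade falls the severe row must be lower, and no planned IGA table would let a reader see why. The exploratory label limits the weight of a p-value but does not tell a reader what it measures.

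**Conclusion.** The point holds as a minor improvement. That success equals IGA 0/1, with a minimum fall of 2 grades from moderate and 3 from severe, is exact under SAP 6.5 and the entry criteria. The moderate-versus-severe row is valid as a description of who reaches clear or almost clear, is tilted against severe patients, and cannot alone show that response differs by severity. The 99% figure needs equal grade-fall distributions with 60% v 20% success and a 220 v 30 split, none of which the documents give. For the other factors the effect arises only where severity mix differs. At the assumed rates it is modest: about 4 points at 10% v 20% severe and 8 points at 10% v 30%. The overall secondary endpoint is unaffected.

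**What to change.** In SAP 6.5 and the Table 7.2.4 series:

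- **(a) Severity.** Add a shift table of baseline IGA (3, 4) by Week-12 IGA (0 to 4). Beside success by baseline IGA, report the proportion with a ≥2-grade decrease as a companion measure, noting that it too depends on baseline. Footnote Table 7.2.4.8 to say that the success comparison reflects reaching 0 or 1, not the amount of improvement.
- **(b) Other factors.** Keep the crude percentages and report beside them a comparison stratified by baseline IGA (Cochran-Mantel-Haenszel) or a logistic model that includes it.
- **(c) Wording.** Align the notes to Tables 7.2.4.3, 7.2.4.7 and 7.5.1, and SAP 2.2, with the ≥2-point definition in SAP 6.5.

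The endpoint does not change and the data are already collected. The cost is one extra table and one stratified test per factor. Severe cells will be sparse in small subgroups (at 10% severe, a subgroup of 125 has about 12 severe patients), so some adjusted comparisons will be imprecise.
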